#### Populations vulnerable to undue influence or coercion

Although not directly targeted, mentally disabled persons, economically or educationally disadvantaged persons, and/or employees or students of the University of Pennsylvania will not be denied enrollment and any special protections and/or additional safeguards will be undertaken in order to protect the rights and welfare of these subjects from coercion or undue influence as appropriate.

#### Subject recruitment

The study recruitment will be accomplished by personal interviews conducted by the PI or study staff during their clinic visit or inpatient hospital admission. Potential subjects will be informed of the criteria for study inclusion, data to be collected during study inclusion, as well as the risks and benefits of study enrollment. The information will be provided in the body of the consent form and presented verbally during the consent process. Consent will be documented by signature of the subject. A copy of the signed consent will then be provided to the subject for their records.

Will the recruitment plan propose to use any Penn media services (communications, marketing, etc.) for outreach via social media avenues (examples include: Facebook, Twitter, blogging, texting, etc.) or does the study team plan to directly use social media to recruit for the research?

No

The following documents are currently attached to this item:

*There are no documents attached for this item.*

#### Subject compensation\*

Will subjects be financially compensated for their participation?

No

**The following documents are currently attached to this item:**

*There are no documents attached for this item.*

**If there is subject compensation, provide the schedule for compensation per study visit or session and total amount for entire participation, either as text or separate document**

Not applicable

---

## **Study Procedures**

### **Suicidal Ideation and Behavior**

Does this research qualify as a clinical investigation that will utilize a test article (ie- drug or biological) which may carry a potential for central nervous system (CNS) effect(s)?

No

### **Procedures**

All patients, 18 years or older, with varying degrees of liver health seen in the Penn Gastroenterology clinic and/or who have been prescribed liver function testing to be drawn the same day as their clinic visit or inpatient hospital admission will be approached for consent. A finger prick will be collected after receiving consent. Blood sample will be tested with Group K's device. These results will be compared to results from a standard hepatic function panel or equivalent test (ALT, AST, ALP, albumin and total protein).

**The following documents are currently attached to this item:**

*There are no documents attached for this item.*

### **Deception**

Does your project use deception?

No

### **Analysis Plan**

Lowest level frequency of detection must be detected 90% of the time. This will become the functional lower limit. The same with the highest level of frequency. We will exclude any data from tests that did not follow standard operating procedures or were not performed in a controlled, laboratory setting as well as any blood that has expired before liver function tests were completed. Each data point will represent one observation or one test run. We will use regression methods to determine the linear relationship between standard lab results and Group K diagnostic's device. We will also determine the correlation coefficient and measure of scatter around the regression line. This will be shown in equation form and in the form of graphs. The dependent variable will be our test results, the independent variable the standard of care.

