#### **Design**

The design of the study is to investigate 200-400 patient finger prick samples to prove the ability of Group Ks Diagnostic app to identify liver function values on the multidiagnostic. The values will be stored on a Penn Server correlating the patient data obtained from the multidiagnostic with a random code, and then the random code correlated to the patient identifier (name and date of birth) and then the patients record of the results of their standard liver function test.

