## **Characteristics of the Study Population**

#### **Target population**

The target population is adults (18 years and old) with varying liver health who have had a hepatic function panel or equivalent tests completed at the same day as their finger prick sample obtained; ALT, AST, ALP, albumin, bilirubin and total protein.

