#### Accrual

The study population will be drawn from adults who have an indication to perform liver function tests during their GI clinic visit or during an inpatient hospital admission. The investigators on this protocol are the Hepatology physicians and therefore will be treating these patients as standard of care. [name] and the research staff will identify subjects.

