#### Key exclusion criteria

1. Inadequate blood sample obtained from finger stick 2. Inconclusive liver function testing 3. Not all 6 liver tests completed on the same sample 4. Liver tests not drawn for normal method at same time as finger stick.

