**Data and Safety Monitoring**

Data will be monitored by the PI and Co-investigator. Any adverse events will be reported to the IRB.

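### The Analysis Plan discards runs under rules that need judgement, one of which conflicts with where testing takes place, and nothing keeps that judgement blind to the laboratory result

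*Protocol*

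**What the plan says.** The exclusion rule is in the protocol's Analysis Plan: "We will exclude any data from tests that did not follow standard operating procedures". The sentence goes on to remove runs that "were not performed in a controlled, laboratory setting as well as any blood that has expired before liver function tests were completed". Key exclusion criteria adds two conditions that can be known only once a sample has been taken or tested: "Inadequate blood sample obtained from finger stick 2. Inconclusive liver function testing".

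The setting is described elsewhere. The Abstract, Study duration and Procedures sections place the finger stick at a clinic visit or during an inpatient admission. The section on resources for human research protection says that subjects are seen in a private clinic room.

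On who holds the two values, Accrual says: "The investigators on this protocol are the Hepatology physicians and therefore will be treating these patients as standard of care". Data and Safety Monitoring says: "Data will be monitored by the PI and Co-investigator". Under Design, the device value carries a random code, with "the random code correlated to the patient identifier (name and date of birth) and then the patients record of the results" of the standard test.

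The primary outcome is the regression curve and correlation coefficient. The Analysis Plan adds a measure of scatter around the line.

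**The concern.** Two features of the exclusion rule combine badly.

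First, it needs interpretation. Whether a run departed from procedure is a judgement unless the procedures define it. The setting clause cannot be applied as written to runs made in a clinic room or on a ward, so someone must decide which of them count.

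Second, nothing in the protocol separates that decision from knowledge of the laboratory result. The investigators can see the panel in routine care, and the study holds both values. The random code is presented under Subject Confidentiality as a privacy measure, not as masking.

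A run that disagrees with the laboratory invites a search for a procedural fault. A run that agrees does not. If exclusions follow that pattern, discordant pairs leave the dataset, and both the correlation and the scatter favour the device. These are the study's main results and, according to the Abstract and Data Disclosure, are intended for an FDA submission.

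**Working it through.** **Step 1: the text side by side.**

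| Question | What the protocol gives |
|---|---|
| Where must a run be done to count? | In a controlled laboratory setting (Analysis Plan) |
| Where are runs done? | Clinic visit or inpatient admission (Abstract, Study duration, Procedures) |
| Who decides on exclusion? | Only an unspecified we (Analysis Plan) |
| When is it decided? | Not stated |
| Is it blind to the laboratory value? | Not stated |
| Are excluded runs counted or re-analysed? | Not stated |

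The first two rows conflict unless clinic rooms and wards are meant to count as such a setting.

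**Step 2: size of the possible effect.** The protocol gives no expected correlation, SD or exclusion rate, so there is no figure of its own to reproduce. The following are assumptions: device = reference + normal error; true r = 0.90; 5% or 10% of runs excluded. With the planned 200 to 400 samples, that is 10 to 20 or 20 to 40 runs.

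If a fraction f with the largest absolute residuals is removed, let c be the normal quantile at 1 − f/2. The residual variance is then multiplied by

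V = 1 − 2cφ(c)/(1 − f),

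and the correlation becomes

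r′ = √[r² / (r² + (1 − r²)V)].

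*All exclusions are the most discordant runs:*
- f = 5%: c = 1.960, φ(c) = 0.0584, V = 0.759. SD ratio = √0.759 = 0.871. r′ = √[0.81/(0.81 + 0.19 × 0.759)] = 0.921.
- f = 10%: c = 1.645, φ(c) = 0.1031, V = 0.623. SD ratio = √0.623 = 0.789. r′ = √[0.81/(0.81 + 0.19 × 0.623)] = 0.934.

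*Half are the most discordant runs and half are random.* The random half has no systematic effect, so the formula applies with f halved:
- 5% excluded, f = 2.5%: c = 2.241, φ(c) = 0.0324, V = 0.851. SD ratio = 0.92. r′ = 0.913.
- 10% excluded, f = 5%: as above, SD ratio = 0.871. r′ = 0.921.

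*Exclusions unrelated to discordance:* V = 1 and r′ = 0.90. Only the number of runs falls.

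**Step 3: simulation check.** 1,500 replicates per cell, with n = 200 and n = 400 (the two agree within about 0.002 in r):

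| True r | Excluded | Unrelated: r (SD ratio) | Half discordant: r (SD ratio) | All discordant: r (SD ratio) |
|---|---|---|---|---|
| 0.80 | 5% | 0.80 (1.00) | 0.82 (0.92) | 0.84 (0.87) |
| 0.80 | 10% | 0.80 (1.00) | 0.84 (0.87) | 0.86 (0.79) |
| 0.90 | 5% | 0.90 (1.00) | 0.91 (0.92) | 0.92 (0.87) |
| 0.90 | 10% | 0.90 (1.00) | 0.92 (0.87) | 0.93 (0.79) |
| 0.95 | 5% | 0.95 (1.00) | 0.96 (0.92) | 0.96 (0.87) |
| 0.95 | 10% | 0.95 (1.00) | 0.96 (0.87) | 0.97 (0.79) |

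The simulation agrees with the formula. Under discordance-driven exclusion the shift always favours the device, and scatter is distorted more than r.

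**The case against.** Excluding invalid runs is ordinary practice, and the operating procedures, which are not shown, may define deviations objectively. Some of the listed conditions leave little room for choice. An inadequate finger-stick sample can be judged at collection, before any reading. Inconclusive testing and expired blood concern the validity of the sample or test, not agreement with the device. Logging of exclusions and sensitivity analyses are often left to a SAP. The protocol sets no acceptance threshold for r or scatter, so no decision can be shown to change.

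Most of this stands, and it narrows the point to the procedure and setting clauses. It does not remove the point. The protocol itself fixes those clauses, and the setting clause conflicts with the protocol's own account of where testing happens.

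Two stronger readings are tempting, but the documents do not support them.

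- *Exclusions are made after the laboratory result is known.* No section gives the order of events or names who applies the rule. That the result could be known is inferred from the treating role and the lack of any masking statement. The app reading, available within 20 minutes according to the Abstract, may well precede the laboratory value. The exposure is in the later decision to discard.
- *Patients can be chosen on a result already known.* Target population does speak of adults "who have had a hepatic function panel or equivalent tests completed", and the inclusion criteria use similar wording. But the Abstract and Procedures describe tests prescribed and still to be drawn that day, and the fourth exclusion criterion requires the standard draw to be made at the time of the finger stick. Taken together, the wording mainly requires that a reference result exists. Loosening it would weaken the inclusion requirement for all six reference tests.

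**Conclusion.** The point holds as a gap and an internal contradiction, not as evidence of biased practice. The setting clause conflicts with the clinic and inpatient setting and, read literally, leaves almost nothing to analyse. Whoever resolves that run by run may have access to both values, and the protocol has no safeguard against this.

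The size cannot be determined from the document, and its range starts at zero. Under the assumed true r of 0.90 with 5% to 10% of runs excluded, the reported r lies between 0.90 (exclusions unrelated to discordance) and 0.93 (10% excluded, all the most discordant). The fall in residual SD lies between 0% and 21%. The upper ends are worst cases. The figures rest on normal errors and on the assumed exclusion rates and mechanisms.

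This should be corrected: it bears on the primary outcome, and the remedy is cheap.

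**What to change.** In the Analysis Plan:

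1. Reconcile the controlled laboratory setting clause with testing at clinic visits and during inpatient admissions, so that it is clear which runs it removes.
2. State that the app value is locked, and every exclusion recorded with its reason under the random code, before the device value is linked to the laboratory value in the study dataset. This governs study linkage only; treating physicians' routine access to results is unaffected.
3. State that all excluded runs are counted and reported by reason, including those removed under the sample-based items in Key exclusion criteria, and that the primary analysis is repeated on every run that has both values.

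Leave the wording on completed tests in Target population and Key inclusion criteria as it is.

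The cost is wording plus one ordering step in data handling. Random codes are already planned, and the form reports no subjects enrolled, so on that status the change can precede all data. The downside is that reported scatter may be slightly less favourable.

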**Objectives****Overall objectives**

1. To obtain regression curves and a correlation coefficient to compare standard blood draws to the investigational diagnostic device.

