**Primary outcome variable(s)**

Regression curve and correlation coefficient

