**Secondary outcome variable(s)**

The consistent accuracy of the diagnostic device

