coverage, and provider. Given that over two-thirds of all clinical decisions are based on laboratory testing (COLA, 2015) and in a 2002 survey of the US, 77% of providers were unable to contact their patients with abnormal diagnostic results (White, 2002), diagnostics are not working efficiently for outpatient providers. These studies show that lack of access to fast point of care results leads to significant problems in continuum of care and effective care. Very few point of care (POC) diagnostics are used by doctors, as modular machines are often cost or workflow prohibitive. Many POC diagnostics require a trained technician and have high cost hardware and certifications. The POC diagnostics that are often used are tests such as pregnancy tests or rapid strep tests that are multiple different platforms and are rate-limited in how many tests a practice can adopt. Group K is revolutionizing healthcare through innovative POC diagnostics. We solve the inefficiencies of current lab solutions by bringing the "lab" to the provider and allowing practitioners to run diagnostic tests onsite in doctors offices and clinics. With a low cost, reliable system providers have actionable information before the patient leaves the office. Doctor offices will be able to pay a low cost for the product and bill insurers for running diagnostics. Group Ks quick, inexpensive, and accurate diagnostic platform will be able to improve care for patients all around the world. Group K is developing a paper microfluidic platform with an accompanying mobile application(app). The paper microfluidic device is a simple, inexpensive wax backed device with three testing areas. These areas have a mix of dried proprietary reagents that when combined with a patients drop of blood, or in the future, saliva or urine, will produce results in a color change. An app is then used to interpret the color change and output results to a doctor.

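### The protocol's outcome is a regression curve, but the Analysis Plan fixes a straight line and gives no rule for checking linearity, so bias that varies by level can go unreported for some response shapes

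*Protocol*

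**What the plan says.** The overall objective is a curve: "To obtain regression curves and a correlation coefficient to compare standard blood draws to the investigational diagnostic device". The primary outcome repeats it: "Regression curve and correlation coefficient". The secondary outcome is "The consistent accuracy of the diagnostic device", with no measure attached.

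The Analysis Plan specifies a line: "We will use regression methods to determine the linear relationship between standard lab results and Group K diagnostic's device". It adds: "We will also determine the correlation coefficient and measure of scatter around the regression line". On display it says: "This will be shown in equation form and in the form of graphs". The axes are fixed: "The dependent variable will be our test results, the independent variable the standard of care".

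The Background explains where the device value comes from. Dried reagents mixed with a drop of blood "will produce results in a color change. An app is then used to interpret the color change and output results to a doctor".

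**The concern.** The objective and primary outcome leave the shape of the relation open, and the Analysis Plan closes it to a straight line. No sentence says how the line is to be tested or what is reported if it does not fit.

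This matters because the study's stated purpose is to show accuracy for a regulatory file. If the average device response bends across the range, the fitted line absorbs the bend into its scatter figure as though it were random error. The slope and intercept describe the line, not the bend. The overall mean difference does not help either, because errors of opposite sign at different levels cancel. The published equation could then be read as evidence of no bias when bias differs by level.

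The device value is an app's reading of a colour change. The protocol gives no evidence that this reading is linear in the analyte and none that it bends, so linearity is assumed without support.

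**Working it through.** **No figure to reproduce.** The protocol states no acceptance limit, error size, analyte distribution or sample-size derivation. It gives only a sample count (Design: 200-400). Every other input below is an assumption.

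**Step 1: what the three numbers can show.** Write the device value as y = f(x) + e, with x the laboratory value. Around the least-squares line a + bx,

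scatter² = mean of (f(x) - a - bx)² + variance of e.

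The scatter figure reports only the sum. The correlation coefficient depends on the same sum: r² = b²Var(x) / (b²Var(x) + scatter²). Least squares also forces the residuals to average zero. If the line comes out as y = x, the overall mean difference is therefore zero whatever the bend.

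**Step 2: a case in which the equation looks unbiased.** Assumptions:
- ALT is log-normal, median 40 U/L, log-SD 0.6, kept to 8-400. This gives mean 48.0 and SD 31.3.
- The raw signal is g = x/(x + 400).
- The output scale was set by a straight-line fit in the same kind of population: y = (g - b0)/b1, with b1 = Cov(x, g)/Var(x) = 0.001773 and b0 = mean(g) - b1·mean(x) = 0.01818.
- Random error is 10% of the value.

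Slope 1.00, intercept 0.0 and mean difference 0.0 follow from this scaling. They are inputs to the example, not results of it. The results are these:
- Random error alone: 0.10 × √(48.0² + 31.3²) = 5.7 U/L. A truly linear device has r = 31.3/√(31.3² + 5.7²) = 0.984.
- With the bend, scatter is 7.0 U/L and r = 31.3/√(31.3² + 7.0²) = 0.976.
- At 20 U/L: g = 20/420 = 0.04762, y = (0.04762 - 0.01818)/0.001773 = 16.6, bias -17%.
- At 60 U/L: g = 60/460 = 0.13043, y = (0.13043 - 0.01818)/0.001773 = 63.3, bias +5.5%.
- About 12% of patients lie below 20 U/L, or 24 to 48 of 200-400. Their bias is -17% or worse.
- Bias is -11% at 200 U/L, but only about 0.4% of patients exceed 200, fewer than two in 400.

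With log-SD 0.8 instead, r is 0.975, and bias is about -29% at 20 and +10.5% at 80 U/L.

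**Step 3: a second shape, with different assumptions.** Laboratory values are uniform on 10-400, the bend is symmetric, and the error SD is 15 or 30. Slope is 1.00 and intercept about 0. The correlation is 0.986 or 0.961, against 0.991 or 0.967 for a linear device. Scatter rises only from 15 to 19, or from 30 to 32. Mean bias by third of the range is about -6, +12 and -6.

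**Step 4: bends that the planned equation would reveal.** With the same uniform range, a saturating response scaled to be correct at 200 gives slope 0.77 and intercept +34. Taking the Step 2 signal and calibrating it at two fixed points gives:

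| Calibration points (U/L) | Slope | Intercept | Mean difference |
|---|---|---|---|
| 10 and 400 | 1.46 | 4.8 | +27 |
| 10 and 200 | 1.09 | 6.1 | +10.5 |
| 20 and 100 | 0.93 | 4.5 | not computed |

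These equations would mostly not look unbiased. A line still misstates the pattern, though. In the uniform-range example mean bias by third is about +12, -2.5 and -49.

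**Step 5: what a check would do.** In the Step 2 scenario, a quadratic term in a regression weighted by 1/x² detected the bend in every simulated study at n = 200 and at n = 400. It flagged a truly linear device in about 5%.

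**The case against.** **The graphs.** A reader might infer that nothing in the plan could show curvature. That is not so: the Analysis Plan promises graphs, and a plot of device against laboratory value can show a bend. What remains is that no rule says how a graph is judged or what follows. With right-skewed values a small absolute error is also hard to see: 17% at 20 U/L is 3.4 units on an axis that may reach 400.

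**The word curve.** A reader might also infer that a straight line is the only model contemplated. The objective and primary outcome say otherwise, so the wording may simply be loose. This stands as a description, and it is itself the reason to reconcile the sections.

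**The statistical analysis plan.** Lack-of-fit tests and residual checks are commonly left to an analysis plan, which is not at hand, and the protocol forbids none of them. The absence of a named diagnostic would be weak ground alone. But the linear model is written into the protocol, and a plan that follows it inherits the mismatch with the primary outcome.

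**The illustration.** The scaling in Step 2 was chosen to hide the bend, and Step 4 shows that other calibrations would not. The large high-end biases concern almost no patients. In the log-SD 0.8 variant the device returns a negative ALT (-3.3) at 8 U/L, which any plot would expose. All of this stands. The example shows that concealment is possible, not that it is likely.

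**Conclusion.** The point holds in limited form. The protocol names a regression curve as its outcome, fixes a line as its method, and reports numbers that cannot tell curvature from random error. For some response shapes, an equation close to slope 1 and intercept 0 with r about 0.98 is compatible with bias of about -17% at 20 U/L and +5.5% at 60 U/L. Those sizes rest wholly on the assumed distribution, saturation constant, scaling and error.

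Two stronger readings are not supported. The first is that this device does respond non-linearly: the documents say only that an app interprets a colour, and the app may already correct for curvature. The second is that readings would be wrong where clinicians act on them: the documents give no decision levels.

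The change is worth making because it is nearly free, and the protocol's status section reports no subjects enrolled.

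**What to change.** Amend the Analysis Plan so that its linear wording agrees with the objective and primary outcome. State that, for each liver test:

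1. Linearity is checked by adding a quadratic or spline term to the regression of device on laboratory value, weighted if the error grows with level.
2. Percentage difference is plotted against laboratory value.
3. Where curvature is found, the fitted curve and the bias at prespecified levels are reported, and the straight-line equation is claimed only over the range in which it holds.

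**Cost:** a little more analysis on data already to be collected, with no extra patients or samples. A truly linear test will be flagged about 5% of the time at the usual 5% level, so the size of the departure should be reported with the test. The linear claim may cover a narrower range for some tests.

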**Modification Summary**

Please describe any required modification to the protocol. If you are using this form to submit an exception or report a deviation, enter 'N/A' in the box below.

This modification is to expand recruitment to include patients admitted to inpatient services at The Hospital of the University of Pennsylvania.

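### One line and one scatter figure per test make no provision for device error that changes with the level of the result

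*Protocol*

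**What the plan says.** The Protocol, Primary outcome variable(s), names "Regression curve and correlation coefficient" as the primary outcome. The Analysis Plan gives the method: "We will use regression methods to determine the linear relationship between standard lab results" and the device. It fixes the direction ("The dependent variable will be our test results, the independent variable the standard of care") and the unit of analysis ("Each data point will represent one observation or one test run"), and it plans one summary of spread: "We will also determine the correlation coefficient and measure of scatter around the regression line". Results are to be shown as an equation and as graphs.

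The same section limits the usable range: "Lowest level frequency of detection must be detected 90% of the time. This will become the functional lower limit". A matching rule applies at the upper end. No values are given for either limit.

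The target population is "adults (18 years and old) with varying liver health", and the current modification is to "expand recruitment to include patients admitted to inpatient services". The inclusion criteria require six tests: ALT, AST, ALP, albumin, bilirubin and total protein. The protocol mentions neither weighting, transformation nor scatter by level. It also states no error model, no distribution for any test and no confidence interval for the slope.

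**The concern.** A single scatter figure around a line describes every patient only if the device error has the same absolute size at every level. The study recruits across a range of liver health, so ALT, AST, ALP and bilirubin may differ many-fold between subjects. The device is a paper colour-change test read by an app, and the protocol gives no reason to expect constant error from normal to very high values.

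If error grows with level, the few highest results dominate the pooled figure. It would then make the device look worse than it is for near-normal patients and better than it is for high results. A fault near the normal range could be lost within scatter produced at the top. This matters because the regression is primary, the secondary outcome is whether the device is consistently accurate, and the results are intended for an FDA submission.

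**Working it through.** The plan has no figure to reproduce: 200 to 400 samples are stated without a derivation, SD or margin. The inputs below are therefore assumptions, except n, which is the upper end of the stated range.

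**Inputs.** ALT log-normal with median 40 U/L and log-SD s = 0.6, 0.8 or 1.0; unbiased device; error SD = 0.15x at laboratory value x; n = 400.

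**Closed form, no range limit.**
- Pooled SD = 0.15 × √E[x²] = 0.15 × 40 × exp(s²) = 6 exp(s²).
- True SD below 40 U/L = pooled × √(Φ(−2s)/0.5).
- True SD above 100 U/L = pooled × √([1−Φ(z−2s)]/[1−Φ(z)]), where z = ln(2.5)/s.
- The pooled and true SDs agree where x = 40 exp(s²), which is percentile Φ(s).

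| s | Pooled SD | True SD below 40 | True SD above 100 | Level of agreement |
|---|---|---|---|---|
| 0.6 | 8.6 | 4.1 | 20.8 | 57 U/L (73rd percentile) |
| 0.8 | 11.4 | 3.8 | 26.3 | 76 U/L (79th) |
| 1.0 | 16.3 | 3.5 | 35.7 | 109 U/L (84th) |

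The pooled figure is 8.6/4.1 = 2.1 to 16.3/3.5 = 4.7 times too large below 40 U/L. Above 100 U/L it is 8.6/20.8 = 0.41 to 16.3/35.7 = 0.46 of the truth. Simulation at n = 400 gives 8 to 15 pooled, about 4 below 40 and 20 to 33 above 100. This is slightly lower at the top because samples of 400 do not always reach the extreme tail.

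**Inside assumed functional limits** (4,000 simulated studies per setting, n = 400):
- 10 to 400 U/L, 15% CV: pooled 8.6 to 13.3, against 3.8 to 4.2 below 40 and 20.7 to 27.4 above 100.
- 10 to 250 U/L, 15% CV: pooled 8.4 to 11.3, against 3.8 to 4.2 and 20.1 to 23.1.
- 10 to 250 U/L, 10% CV plus a constant SD of 5: pooled 7.5 to 9.1, against 5.6 to 5.7 (1.3 to 1.6 times too large) and 14.3 to 16.2 (0.52 to 0.56 of the truth).

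Limits and a constant error component shrink the distortion but do not remove it.

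**Constant error (SD 5).** The pooled SD is 5.0 and is right at every level.

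**Narrow-range tests** (log-SD 0.10 to 0.15, 5% CV, as might suit albumin and total protein). The pooled figure is within about 25% of the truth from the 10th to the 97.5th percentile.

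**If a slope interval were added to an ordinary least-squares line.** Without range limits, nominal 95% coverage is 25 to 70% under proportional error (CV 10 to 20%, log-SD 0.5 to 1.2), 36 to 55% with 10% CV plus SD 5 (log-SD 0.8 to 1.0), and 95% under constant error. Heteroscedasticity-robust (HC3) standard errors gave 93 to 95% in all the settings simulated here.

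**The case against.** The strongest case against is that the Analysis Plan says only that regression methods will be used. Weighting, a log scale or banded scatter would contradict nothing in it, and a statistical analysis plan that is not shown could supply them. This stands as far as weighting goes. It stands less well for the scatter, because one figure around one line is a stated summary that could mislead, not a detail left open.

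A reader might infer more: that the line is unweighted, that it covers the whole range, that its slope interval is far too narrow and that the scatter is wrong at every level. The documents do not support this.
- Neither least squares nor an unweighted fit is stated.
- The Analysis Plan restricts the range at both ends.
- No slope interval is planned, so the coverage figures describe an analysis that the protocol does not contain.
- Even under proportional error the pooled SD is right at one level, and under constant error it is right everywhere.
- High leverage is not a fault in itself. At log-SD 0.8 the most extreme 5% of points carry about 60% of the slope information even under constant error, where least squares is efficient.

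It is also tempting to prescribe weights of one over the squared laboratory value. With a constant error component and no range limit, that fit covers only 59 to 79%, and its slope SD is 1.2 to 3.5 times that of ordinary least squares.

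Finally, the planned graphs would show fanning scatter to anyone who looks. That reduces the risk of concealment but does not correct the reported figure.

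**Conclusion.** The concern holds in a limited, conditional form. The protocol fixes a single line and a single scatter measure as its summary and does not provide for error that varies with level. For ALT, AST, ALP and bilirubin, if error is proportional at about 15% CV and the values are skewed as assumed, the single figure is roughly two to four times too large below 40 U/L at n = 400. Above 100 U/L it is a little under half the true value. With a constant error component and range limits the distortion is milder, and with constant error there is none. The direction of the effect is secure if error grows with level. Its size is not, because the documents give neither an error model nor a distribution. This is a worthwhile improvement to the stated analysis, not a flaw that invalidates the study.

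**What to change.** In the Analysis Plan, for ALT, AST, ALP and bilirubin and within the functional limits:

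1. Report scatter and bias in preset bands of the laboratory value, in units and as % CV, beside the overall figure.
2. Check residual spread against level. Where it is not constant, fit with weights taken from the observed error pattern or on the log scale.
3. Use heteroscedasticity-robust standard errors for any slope interval that is reported.
4. Do not fix one-over-squared weights in advance.

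Leave albumin and total protein as planned.

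The cost is a few sentences and a few more figures per test. No extra data are needed, and the protocol's status section records no subject enrolled. Each banded figure is less precise than the pooled one. As an illustration, with bands cut at 40 and 100 U/L under the assumptions above, the top band would hold about 25 to 72 of 400 subjects. The relative standard error of its SD would be about 1/√(2×24) = 14% to 1/√(2×71) = 8%. Banded reporting is valid whichever error pattern applies.
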